6.3.5. Radiation Treatment

If clinically indicated, palliative radiation therapy to non-target lesions is permitted but study drugs should be held for 3-5 days before the start of palliative radiation therapy and 3-5 days after palliative radiation therapy.

6.4. Study Drug Administration

6.4.1. Elotuzumab Administration

Elotuzumab for Injection is supplied as a lyophilized product in single-use 400mg and 300mg vials. Each vial of Elotuzumab for Injection, 400 mg/Vial and Elotuzumab for Injection, 300 mg/Vial should be reconstituted with sterile water for injection (SWFI) at the clinical compounding site. Once the reconstitution is completed, dilution with 0.9% sodium chloride injection (NS) is necessary to result in an elotuzumab concentration from 1.0 mg/mL to no higher than 6.0 mg/mL. The dose for C1D1 will be calculated using the screening weight. Dose adjustments do not need to be made for weight gains/losses of ≤ 10%.

Elotuzumab will be given as an IV infusion and should be initiated at a rate of 0.5mL/min. If well tolerated, the infusion rate may be increased in a stepwise fashion as described in the table below. The maximum infusion rate should not exceed 5mL/min.

- Cycle 1-2: 10mg/kg on days 1, 8, 15, and 22 of a 28-day cycle
- Cycles 3+: 10mg/kg on days 1 and 15 of a 28-day cycle

Infusion Rate for Elotuzumab

Cycle 1, Dose 1		Cycle 1, Dose 2		Cycle 1, Dose 3 and 4 And all subsequent Cycles
Time Interval	Rate	Time Interval	Rate	Rate
0 - 30 min	0.5 mL/min	0 - 30 min	3 mL/min	
30 - 60 min	1 mL/min	≥30 min	4 mL/min ^a	5 mL/min ^a
≥60 min	2 mL/min ^a	-	-	

All subjects should have vital signs monitored at the start and end of the infusion. If a subject experiences any significant medical event, then the investigator should assess whether the subject should stay overnight for observation. If the subject has not experienced a significant medical event but is hospitalized overnight only for observation, then the hospitalization should not be reported as a serious adverse event.

The sponsor may modify the infusion rates or the preinfusion medications (Section 6.1.3.1) prospectively based upon the information collected to date from this and other studies. Additional details for administration times and rates, as well as preinfusion medications, will be provided in the administration guidelines.

6.4.2. Carfilzomib Administration

Carfilzomib for Injection is supplied as a lyophilized parenteral product in single-use vials. The lyophilized product is reconstituted with Water for Injection to a final carfilzomib concentration of 2.0 mg/mL prior to administration. The dose will be calculated using the subject's actual BSA at baseline. Subjects with a BSA > 2.2 m² will receive a dose based upon a 2.2 m² BSA. Dose adjustments do not need to be made for weight gains/losses of \leq 10%. Subjects with a Body Surface Area (BSA) of greater than 2.2 m² will receive a capped dose of 44 mg of carfilzomib (at the 20mg/m^2 dose level), 123.2mg of carfilzomib (at the 56mg/m^2 dose level), or 154 (at the 70mg/m^2 dose level).

Carfilzomib will be given as an IV infusion over 30 minutes on Days 1, 8, and 15 of a 28-day cycle. If the subject has a dedicated line for carfilzomib administration, the line must be flushed with a minimum of 20 mL of normal saline prior to and after drug administration. The dose will be administered at a facility capable of managing hypersensitivity reactions. Subjects will be prehydrated with 250mL normal saline or other appropriate IV fluid formulation on cycle 1 Day 1. Other hydration procedures will be optional and per the discretion of the treating physician. Subjects will remain at the clinic under observation for at least 1 hour following each dose of carfilzomib in Cycle 1 and following the dose on Cycle 2 Day 1. Subjects should be monitored periodically during this period for evidence of fluid overload. Serum chemistry values, including creatinine, must be obtained and reviewed prior to each dose of carfilzomib during Cycles 1 and 2. Refer to Table 6-1 for guidance regarding dose reduction in subjects with compromised renal function.

Doses of carfilzomib may be rescheduled up to 2 days if the scheduled day falls upon a holiday or with approval from the Lead Principal Investigator. Missed doses will not be replaced during a cycle. Carfilzomib will be escalated from 20mg/m^2 (Cycle 1 Day 1) to 56mg/m^2 (Cycle 1 Day 8 and 15 see below) and then further escalated to 70mg/m^2 (Cycle 2 Day 1) as long as the subject does not present with cytokine release symptoms (fever, rash, dyspnea, etc) after Cycle 1 Day 2.

- Cycle 1: 20 mg/m² Day 1; 56 mg/m² Day 8; 56mg/m² Day 15.
- Cycles 2 8: 70mg/m^2 if tolerated Days 1, 8, and 15
- Cycles 9+ (for up to 24 cycles max): 70mg/m² if tolerated Days 1 and 15

Subjects will continue on E-KRd regimen for 12 cycles. MRD results after cycles 8 and 12 will determine the course of action after C12 with 3 possible outcomes: 1) subjects who are MRD- at both instances will end E-KRd and will continue on E-Rd maintenance until disease progression. 2) Subjects who are MRD+ after cycle 8 but MRD- after cycle 12 will receive 6 additional E-KRd cycles (for a total of 18) and then continue on E-Rd maintenance until disease progression. 3) Subjects who are MRD+ at both instances will receive 12 additional E-KRd cycles (for a total of 24) and continue on E-Rd maintenance until disease progression.

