Study Design	This study will be a multi-center, open-label, Phase 2 study. Those newly diagnosed with MM requiring systemic chemotherapy will be eligible for enrollment. Dose Schedule and Dose Levels in 28-day cycles		
	Subjects will be tested for Minimal Residual Disease (MRD) by Next Generation Sequencing (NGS) and flow cytometry after cycles 8 and 12. A treatment decision will be made after cycle 12 based on these results. There are three possible outcomes based on the IFM trial (Avet-Loiseau et al., 2015): 1) if the subject is MRD-negative by NGS after cycle 8 and 12, the subject will be go on E-Rd maintenance until disease progression. 2) If the subject is MRD-positive after cycle 8 but MRD-negative after cycle 12, 6 more cycles of E-KRd will be given and at the end of 18		

cycles, the subject will go on E-Rd maintenance until disease progression. 3) Finally, if the subject is MRD-positive at both instances, 12 additional cycles of E-KRd will be given and at the end of 24 cycles total, the subject will go on E-Rd maintenance until disease progression. For subjects for whom NGS evaluation is not successful because of inadequate calibration specimen or not-evaluable follow-up specimen, the results of MRD testing by flow will be used for treatment decisions.

Elotuzumab

Cycle 1-2 Days 1, 8, 15, 22	Cycle 3+ Days 1 and 15
10 mg/kg IV infusion weekly	10 mg/kg IV infusion every 2
starting Cycle 1 day 1	weeks starting Cycle 3 day 1

^{*} On days when elotuzumab and carfilzomib coincide, carfilzomib will be infused first followed by elotuzumab infusion

Carfilzomib

Cycle 1*	Cycle 2-8	Cycle 9+
IV infusion Day 1: 20 mg/m ² Day 8 & 15: 56 mg/m ²	IV infusion 70 mg/m ² : Days 1, 8, and 15	IV infusion Last tolerated dose on Days 1 and 15

^{*}Dose escalation may need to be modified based on toxicities in the prior week. Please see dose modifications section.

Lenalidomide

Cycle 1-8	Cycle 9+
PO at 25 mg per dose on Days 1-	PO at last tolerated dose for days
21	1-21

Dexamethasone

Cycle 1-2

Tx Days 1, 8, 15	Tx Days 2, 9, 16	Tx Day 22
20 mg IV no more than 3 hrs prior to elotuzumab infusion	20 mg PO the day after elotuzumab infusion	40mg IV (C1 only) or PO, no more than 3 hrs prior to elotuzumab infusion

Cycle 3-4

Tx Days 1, 8, 15, 22

40mg PO weekly. On days when dexamethasone and elotuzumab coincide, dexamethasone should be taken no more than 3 hours prior to elotuzumab infusion

Cycle 5+

Tx Days 1, 8, 15, 22

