We hypothesize that treatment with E-KRd will improve the rate of sCR and/or the rate of negative MRD by next generation gene sequencing (NGS) by clonoSEQ (Adaptive Biotechnologies) at the end of 8 cycles among non-transplant candidates or transplant candidates who agreed to defer transplant compared to historical results of KRd alone. We would like to investigate this in the proposed study, in subjects who are newly diagnosed and who are transplant ineligible or those who are transplant-eligible, and choose to delay transplant. The primary efficacy endpoint will be the rate of sCR and/or the rate of negative MRD by NGS at the end of 8 cycles among non-transplant candidates and/or transplant candidates who agreed to defer transplant.

Among secondary objectives, we propose to evaluate the status of MRD disease at established landmark time-points, and to use MRD status to determine the duration of E-KRd treatment. We anticipate that E-KRd treatment will result in a statistically improved rate of MRD-negative disease compared to the MRD rate observed in subjects who were treated with KRd in the historical trial.

Based on the results from the IMF study (Avet-Loiseau et al., 2015) we propose to use different durations of E-KRd treatment using MRD status as the modifying criteria. There will be 3 possible outcomes:

- 1) Subjects who have MRD-negative disease at the completion of 8 and 12 cycles of E-KRd will receive a shorter duration of E-KRd treatment (for a total of 12 cycles) and continue on E-Rd maintenance until disease progression.
- 2) Subjects that are MRD-positive after cycle 8 but transform to MRD-negative after 12 cycles of E-KRd will receive an additional 6 cycles of E-KRd and then continue on E-Rd maintenance until disease progression.
- 3) Subjects that are MRD-positive after 8 and 12 cycles, will receive an additional 12 cycles of E-KRd and then continue on E-Rd maintenance until disease progression.

To make safety the highest priority, the protocol will (1) incorporate scheduled dose reductions of dexamethasone and will (2) provide aggressive required dose modifications with the emergence of any treatment related toxicities greater than G1.

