4.2. Study Procedures

On cycles 1 and 2, subjects will receive elotuzumab weekly on days 1, 8, 15, and 22 of a 28-day cycle at 10mg/kg. From cycle 3 onward, elotuzumab will be dosed every other week on days 1 and 15 at 10mg/kg.

Carfilzomib will be dose escalated on cycle 1 as follows: 20 mg/m^2 on day 1, 56mg/m^2 on day 8, and 56mg/m^2 on day 15. Between cycles 2-8, carfilzomib will be given on days 1, 8, and 15 of a 28-day cycle at 70 mg/m². From cycle 9 onward, carfilzomib will be given at the best-tolerated dose on days 1 and 15 of a 28-day cycle. Splitting carfilzomib dose to 27 mg/m^2 on days 8, 9 and 36 mg/m^2 on days 15, 16, and in subsequent cycles on days 1, 2, 8, 9, 15, 16 - as in the original KRd 2-day weekly schedule – will be allowed based on discussion with the lead PI.

Lenalidomide will be given initially at 25mg per dose daily on days 1-21 of a 28-day cycle for cycles 1-8. From cycle 9 onward, lenalidomide will be dosed at last tolerated dose daily on days 1-21 of a 28-day cycle.

Dexamethasone will initially be give 40 mg weekly (cycles 1-4), which in the first cycle will be split into two doses as follows: 20mg of dexamethasone will be given IV on days 1, 8, and 15 no more than 3 hours prior to elotuzumab infusion and 20mg on days 2, 9, and 16 will be taken PO. If in the course of dose modification carfilzomib is split, dex will be given prior to carfilzomib. However, most pts will not be given carfilzomib on days 2, 9, and 16. On Day 22 of cycle 1,

40mg dexamethasone will be given IV no longer than 3 hours prior to elotuzumab. In cycles 2-4 40mg dexamethasone will be taken PO (or IV) on days 1, 8, 15, and 22. On days when dexamethasone coincides with elotuzumab, dexamethasone will be taken no longer than 3 hours prior to elotuzumab infusion. For cycles 5+ dexamethasone will be reduced to 20 mg PO or IV weekly.

Dose modifications will be mandated based on aggressive schedule of dose modification for toxicities as per specific guidelines. Otherwise, subjects will continue at their best tolerated dose of lenalidomide on days 1-21 and their best tolerated dose of carfilzomib on days 1, 8, 15 in cycles 1-8 and days 1, 15, in cycles 9-12 (in subjects with MRD- disease at the end of cycle 8 and 12) or cycles 9-18 (in subjects with MRD+ disease at the end of cycle 8 but MRD- at the end of cycle 12) or cycles 9-24 (in subjects with MRD+ disease at the end of cycle 8 and 12). See section 1.7.

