All subjects will have weekly visits for toxicity assessments in the first cycle and then monthly from cycles 2+. Disease assessments will start on Cycle 1 Day 15 and then will be done on clinic visits on day 1 of each cycle. Treatment will continue on protocol for up to 24 months or if elotuzumab, carfilzomib and lenalidomide are permanently discontinued. Toxicity will be graded using the National Cancer Institute Common Terminology Criteria for Adverse Events version 4. Subject who complete 12 cycles (who are MRD-negative at the end of cycle 8 and 12), 18 cycles (who were MRD-positive at the end of cycle 8 but MRD-negative at the end of cycle 12), or 24 cycles (who were MRD-positive after cycle 8 and 12) of E-KRd, will then continue elotuzumab, lenalidomide, dexamethasone (E-Rd) maintenance. This regimen will continue until there is progression of the disease or the toxicities require discontinuation of the drug.

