6.4.5. Maintenance treatment

Subjects that complete 12 cycles (who were MRD-negative after cycles 8 and 12), 18 cycles (who were MRD-positive after cycle 8 but MRD-negative after cycle 12), or 24 cycles (who were MRD-positive after cycle 8 and 12) of E-KRd, will continue a regimen of E-Rd until disease progression. This regimen will have elotuzumab every four weeks, lenalidomide at best-tolerated dose (days 1-21), and low dose dexamethasone (weekly) in 28-day cycles until disease progression.

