- 24. On cycles 3-4 40mg dexamethasone will be taken PO on days 1, 8, 15, and 22. On days when dexamethasone coincides with elotuzumab, dexamethasone will be taken no longer than 3 hours prior to elotuzumab infusion. On days when dexamethasone coincides with carfilzomib, dexamethasone will be taken between 30min and 4 hours prior to carfilzomib infusion. When dexamethasone, carfilzomib and elotuzumab coincide, dexamethasone will be dosed first, followed by carfilzomib infusion, and finally elotuzumab will be infused. On cycles 5+ 20mg dexamethasone will be taken PO on days 1, 8, 15, and 22. On days when dexamethasone coincides with elotuzumab, dexamethasone will be taken no longer than 3 hours prior to elotuzumab infusion. On days when dexamethasone coincides with carfilzomib, dexamethasone will be taken between 30min and 4 hours prior to carfilzomib infusion. When dexamethasone, carfilzomib and elotuzumab coincide, dexamethasone will be dosed first, followed by carfilzomib infusion, and finally elotuzumab will be infused.
- 25. End of treatment will vary depending on MRD results post cycle 8 and 12. Subjects that are MRD negative after cycle 8 and 12, will go on E-Rd maintenance until disease progression, subjects that are MRD+ after cycle 8 but MRD- after cycle 12, will get another 6 cycles of Elo-KRd and go on E-Rd maintenance until disease progression; and subjects that are MRD+ at both instances will be given another 12 cycles of Elo-KRd and go on E-Rd maintenance until disease progression
- 26. Subjects will be followed for survival and development of any new cancers, at least every 3 months for up to 6 years from start of treatment. Reports of any death should include date of death and specific cause (disease under study or specify other cause).
- 27. Assessment for disease progression in subjects who did not progress during treatment. Every 3 months (+/- 30 days) from safety follow-up visit (28 days post-last study treatment or ASCT, if applicable) for up to 6 years from enrollment.
- 28. A CT-PET must be performed to confirm MRD-negative disease per Standard of Care. Subjects who are MRD-positive do not need PET scans until suspected CR. MRD-negative subjects will undergo a yearly PET until progression. If there is clinical need for assessment at cycles 8 and 12, a CT-PET should be performed at these timepoints as well.

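### Does the MRD-guided duration rule need a fourth branch for subjects who are MRD-negative after cycle 8 but MRD-positive after cycle 12?

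*Combined protocol and SAP*

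**What the plan says.** The rule appears in seven places. The Synopsis (Study Design) introduces it with "There are three possible outcomes based on the IFM trial", Section 1.6 with "There will be 3 possible outcomes", and Section 6.4.2 with "MRD results after cycles 8 and 12 will determine the course of action after C12 with 3 possible outcomes". Section 4.2 states it twice, once as a carfilzomib schedule and once as the entry point to E-Rd maintenance. Section 6.4.5 repeats it, ending with "24 cycles (who were MRD-positive after cycle 8 and 12". Footnote 25 of Appendix 6 gives it under "End of treatment will vary depending on MRD results post cycle 8 and 12".

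All seven list the same three patterns and durations, and none has a clause for remaining cases. The course before the decision is common to everyone: "Subjects will continue on E-KRd regimen for 12 cycles". NGS decides MRD status; flow cytometry is used only where NGS fails (Synopsis, Section 4.2).

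**The concern.** Three of the statements count the outcomes as three, so the rule reads as complete when it is not. A negative result at cycle 8 need not last, and every subject still on treatment is retested at cycle 12, so the missing pattern can occur. Appendix 4 does not count MRD conversion as progression, so the conversion alone would not take the subject off treatment.

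MRD-guided duration is the adaptive part of the treatment plan. If one pattern has no instruction, the five centers might treat similar subjects differently, and the difference would enter the exposure, safety and later follow-up data.

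**Working it through.** **1. The four patterns.** Cycles last 28 days. Carfilzomib is given on days 1 and 15 from cycle 9 (Section 6.4.2). Elotuzumab is given twice per cycle during E-KRd and once per cycle during E-Rd (Sections 6.4.1 and 6.4.5).

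| After C8 | After C12 | E-KRd total | Further cycles | Days | Carfilzomib infusions after C12 | Elotuzumab infusions, C13–24 |
|---|---|---|---|---|---|---|
| − | − | 12 | 12 − 12 = 0 | 0 | 0 | 12 × 1 = 12 |
| + | − | 18 | 18 − 12 = 6 | 6 × 28 = 168 | 6 × 2 = 12 | 6 × 2 + 6 × 1 = 18 |
| + | + | 24 | 24 − 12 = 12 | 12 × 28 = 336 | 12 × 2 = 24 | 12 × 2 = 24 |
| − | + | not stated | – | – | – | – |

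Lenalidomide and dexamethasone continue in E-Rd on every course, so the open items are carfilzomib and the elotuzumab frequency.

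**2. Whether other text supplies a default.** The 24 months in Section 4.2 and the 24 cycles in Section 6.4.2 are ceilings. Sections 6 and 6.1 describe all four drugs until progression for every subject; read as a default, they would contradict the 12- and 18-cycle courses. The Synopsis moves subjects to E-Rd after E-KRd without an MRD condition. Section 4.2 points to Section 1.7 for the rule, but the rule is in Section 1.6, which is a clerical slip. No default follows.

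**3. Which analyses depend on the decision.**
- Primary test, end of cycle 8 (Section 10.2.1): n = 40, reject at 17 or more. P(X ≥ 17 | 0.30) = 0.063, within the 0.10 level. P(X ≥ 17 | 0.50) = 0.866, which agrees with the stated power of a little over 85%. It is read before the decision.
- sCR test in Section 10.2.2: end of cycle 4, also before the decision.
- PFS, TTP and OS: all subjects with at least one dose. DOR: responders. None of these populations is defined by duration group.
- MRD at 24 months and yearly: scheduled for all subjects, whatever their course.

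**4. How many subjects.** The documents give no conversion rate, so the rate c is an assumption. The proportion p negative at cycle 8 is set at the plan's 30% null and 50% target. Those rates belong to the combined sCR and/or MRD endpoint, and 50% is not an upper bound. With all 40 tested twice, the expected number is 40 × p × c and the chance of at least one is 1 − (1 − pc)^40.

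| p | c | Expected | Chance of at least one |
|---|---|---|---|
| 0.30 | 0.02 | 0.24 | 21% |
| 0.30 | 0.10 | 1.2 | 70% |
| 0.50 | 0.10 | 2.0 | 87% |
| 0.50 | 0.20 | 4.0 | 98% |

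If only 80% reach cycle 12 (also an assumption), 0.24 and 2.0 become 0.24 × 0.8 = 0.19 and 2.0 × 0.8 = 1.6.

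**5. Weight of one subject.** One subject among 40 is 1/40 = 2.5 percentage points of a later MRD rate, and that only if the choice of course changes the subject's status. At the 90% confidence level of Section 10.2.2, a 50% rate in 40 subjects has a half-width of about 1.645 × √(0.25/40) = 0.13, or 13 points.

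**The case for a change.** The best case for amending is practical. Section 1.6 makes MRD status the criterion for E-KRd duration, and Section 7 sends the cycle 12 sample straight to the NGS laboratory so that the result is back in time for that decision. For this pattern the result arrives and no instruction follows. The pattern may even arise without biological change: if NGS fails at cycle 8 and flow reads negative, a positive NGS result at cycle 12 produces it. Each such subject needs a decision, and a fourth line of text costs little.

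The incompleteness stands, and so does the absence of a default. Four further claims do not:

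- Silence does not permit any course from 12 to 24 cycles. The 12-cycle course is written for subjects negative twice and the 18-cycle course for positive then negative. The 12-cycle span is only the distance between the shortest and longest written courses.
- Such a subject does not necessarily stay on treatment. Section 6.9 lists removal reasons other than progression, including the treating investigator's judgment.
- Limiting the cycle 18 sample to positive-then-negative subjects is a separate matter. Subjects positive at both visits have an assigned course and also lack that sample.
- Whether flow replaces NGS at one visit or both is likewise a separate reading question. The text reads naturally as replacing the test that failed.

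Divergence between centers is possible but limited. The lead site coordinates the trial, and Section 13.7 provides a bi-weekly multi-institutional review. The lead-investigator approvals in Section 6.6 concern dose changes and toxicity, so they are not a written authority for this case, but the route for a consistent decision exists.

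**Conclusion.** No change to the plan follows. This is a missing detail in a treatment rule. It is not an error in the design or the analysis: no stated duration is wrong, the seven statements agree with one another, and both hypothesis tests are complete before the rule takes effect. A fourth branch would improve no estimate and no operating characteristic. The choice of course for this pattern is clinical, and none is suggested here.

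The size is probably a handful of subjects at most: 0.24 to 2.0 expected at 2% to 10% conversion, and up to 4.0 at 20%. These counts rest on assumed conversion rates and on the plan's 30% and 50% rates standing in for the cycle 8 MRD-negative rate, which Section 10.2.2 says is not established. Exposure and later follow-up in those subjects could differ with the course chosen, and a report can describe that case by case. The conclusion also assumes that the lead investigator handles such cases consistently.

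An amendment might also come too late. Section 4.2.3 plans a start in Q4 2016 and 12 to 18 months of enrolment. The end of 2016 plus 18 months plus 336 days falls before mid-2019, whereas this version is dated March 2020. Actual accrual is not in the documents, so this is supporting evidence only.
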